or inadequate recovery, including the gastrocnemius and tibialis anterior muscles around the ankle. Muscle weakness or incomplete ligament healing can lead to insufficient joint support, resulting in loss of ankle stability, which is also an important factor in inducing CAI [9,10]. Moreover, the ability of nerves to control muscle movement may be affected, leading to inadequate muscle coordination and increasing the risk of ankle instability [11]. Therefore, strengthening training for the strength and stability of the ankle joint after rehabilitation is particularly important.

Blood Flow Restriction Training (BFRT) is a special training technique aimed at limiting blood flow by using cuffs or elastic bands on the limbs to promote muscle growth and improve strength [13]. BFRT was originally designed for rehabilitation injured athletes because it can improve muscle strength while reducing load, helping to avoid further injuries during the rehabilitation process [14]. But as research deepens, it is gradually being applied to a wider range of fitness and training fields [15,16]. One major advantage of BFRT is that it allows for efficient training under relatively light loads, reducing the burden on joints and tendons, making it suitable for people who find it difficult to withstand high-intensity training due to injuries or other reasons [14]. Meanwhile, BFRT also has the characteristic of achieving muscle growth and strength growth in a short period of time, and it is considered a time-saving training method [14]. BFRT can not only be used for strength training, but also for rehabilitation, improving endurance, and improving sports performance, making it have potential applications in various fields [15]. In rehabilitation training, it can be applied to multiple body parts to promote the recovery of injured areas and improve muscle strength, including; Direct effects on limb muscle groups and elbow and knee joints, indirect effects on shoulders, hips, and buttocks [17, 18, 19, 20], among which studies have shown that BFRT has an activating effect on the calf muscle group of CAI athletes. Under low load resistance exercise, the oxygen saturation of the calf muscle group is significantly reduced, and the muscle fatigue perception score is significantly improved, which has an impact on the strength of the lower limbs of CAI patients There is a promoting effect in terms of functionality and other aspects [21, 22, 23].

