## Research process and methods

Method; Select 30-45 subjects with unstable, restricted, or uncomfortable ankle joints as observation subjects, and randomly divide them into ankle joint blood flow restriction training combined with IASTM group (n=10-15), ankle joint blood flow restriction training alone (n=10-15), and traditional ankle strength training (n=10-15). The intervention lasted for 4-6 weeks, once a week. Cumberland ankle instability assessment, FAAM ankle function assessment score, and ankle range of motion measurement were performed at three time points before intervention, after the first intervention, and after 4 weeks/6 weeks of intervention for the three groups. The ankle strength test was only compared and analyzed at two time points before and after intervention.

Process: This study is divided into three stages: pre intervention stage, post initial intervention stage, and post intervention stage. In the pre intervention stage, researchers will conduct preliminary evaluations and data statistics on subjects, including Cumberland ankle instability assessment, FAAM ankle function assessment score, and ankle range of motion measurement. During the intervention phase, participants from each group will undergo a 6-week exercise intervention, with a training frequency of 2 sessions per week and each session lasting 20-30 minutes. During BFRT exercise, a cuff will be wrapped around the proximal one-third of the upper limb of the subject to improve muscle strength and endurance by restricting blood flow. In this state, corresponding ankle training movements (stability training, ankle peripheral muscle group training) will be completed.

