#### 研究过程及方法

方法;选取30-45名踝关节不稳定、受限或不适受试者作为观察对象,并随机分为踝关节的血流限制训练联合IASTM组(n=10-15)、单纯踝关节的血流限制训练(n=10-15)、传统的踝力量训练(n=10-15)。干预共4-6周,每周一次。分别对三个组干预前、首次干预后、4周/6周干预后三个时间点进行Cumberland踝关节不稳度评估、FAAM踝关节功能评估评分、踝关节运动范围测量。而踝关节力量测试只在干预前后两个时间点进行对比分析。

过程:本本研究分为3个阶段:干预前阶段,首次干预后、干预后阶段。在干预前阶段,研究人员将对受试者进行初步评估和数据统计,包括 Cumber land 踝关节不稳度评估、 FAAM 踝关节功能评估评分、踝关节运动范围测量。在干预阶段,将对各个组的受试者进行为期6周的运动干预,训练频率为2次/周,每次训练20-30分钟。在 BFRT 运动过程中,受试者的上肢近端1/3 处将缠上袖带,通过限制血液流动来达到提高肌肉力量和耐力的效果,在此状态下完成相应的踝关节训练动作(稳定训练、踝关节周围肌群训练)。

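### The only cuff site given for blood flow restriction training, in English and in Chinese, is the arm, although the training and its rationale concern the calf and ankle.

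*Combined protocol and SAP*

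**What the plan says.** Research process and methods states that during BFRT "a cuff will be wrapped around the proximal one-third of the upper limb of the subject". It continues: "In this state, corresponding ankle training movements (stability training, ankle peripheral muscle group training) will be completed". The Chinese counterpart, 研究过程及方法, gives the same location: "受试者的上肢近端1/3 处将缠上袖带".

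The same two sections name the arms by the joint being treated. The BFRT-only arm is "ankle joint blood flow restriction training alone (n=10-15" in English and "单纯踝关节的血流限制训练(n=10-15" in Chinese, and the combined arm carries the same ankle-joint label with IASTM added.

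The background under Basic information bases the use of BFRT in chronic ankle instability on local effects in the leg. During low-load exercise "the oxygen saturation of the calf muscle group is significantly reduced", and BFRT "has an impact on the strength of the lower limbs of CAI patients".

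**The concern.** Flow restriction acts on the limb that is cuffed. A cuff on the arm does not restrict flow to the calf muscles that these exercises train, so the procedure as written does not deliver the intervention that the arm names and the background describe.

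The Control Group section gives the control arm the same training plan as the experimental group. Flow restriction of the trained muscles is therefore the intended difference between BFRT alone and control, and BFRT is the subject of the trial's title. If the cuff is in the wrong place, that comparison no longer asks its question. If practice differed from the text, or varied between operators, a reader cannot tell from the document which intervention was given.

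**Working it through.** The plan gives no figure to reproduce. The check is a comparison of texts, followed by a count of how much of the trial the instruction governs.

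**Every place that bears on cuff position**

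- Project Summary and Basic information: BFRT in general uses cuffs or bands on the limbs. No site is given for this trial.
- Research process and methods: proximal third of the upper limb.
- 研究过程及方法: 上肢近端1/3, which is also the proximal third of the upper limb.
- Experimental Group: lists the exercises done with BFRT and gives no site.

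The upper limb is thus the only trial-specific site in the supplied text. Because the Chinese agrees with the English, an error in the English translation alone does not explain it. A slip of one character in the Chinese source, 上肢 (upper limb) for 下肢 (lower limb), carried into both versions would explain it.

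**Could a remote effect from the arm be intended?** The background does mention remote effects, but those it lists are "indirect effects on shoulders, hips, and buttocks". It names no effect of an arm cuff on the calf or ankle, and its case for ankle instability rests on the calf itself.

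**Consequence for each contrast**

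| Contrast | All operators cuff the exercised leg | Text followed literally |
|---|---|---|
| BFRT alone vs control | Intact | Loses its intended active difference |
| BFRT + IASTM vs control | Intact | Loses the BFRT component; still differs by IASTM |
| BFRT + IASTM vs BFRT alone | Intact | Still differs by IASTM, but the trained muscles are flow-restricted in neither arm |

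**Reach of the instruction** (arm sizes and schedules from Research process and methods)

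- Participants: 2 BFRT arms × 10 = 20, and 2 × 15 = 30, out of 30-45. This is two thirds of the trial (20/30 = 30/45).
- Sessions under the process paragraph (2 per week for 6 weeks): 2 × 6 = 12 each; 20 × 12 = 240 to 30 × 12 = 360 in total.
- Sessions under the method paragraph (once a week for 4-6 weeks): 4 to 6 each; 20 × 4 = 80 to 30 × 6 = 180 in total.

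The two session totals differ because the section states two training schedules, which is a separate matter. These counts show how often the instruction applies. They do not measure bias or lost effect.

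**The case against.** The strongest reply is that this is an evident slip that nobody would follow. The arm names, the calf rationale and the exercises all point to the leg, and nothing in the document shows that any operator cuffed an arm. All of the damage to the contrasts depends on literal compliance, for which there is no evidence either way.

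Much of this stands. The error is better read as a drafting slip than as a deliberate design, and the effect on the contrasts is conditional. Two narrower points also stand. Some pages are absent from the supplied text, so the statement that no other site is given applies to that text only. The background's list of remote effects is introduced as a list of examples, so the fair statement is that it names no arm-to-ankle effect, not that none could be argued.

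The need to correct the text remains. This is the sole operative instruction for placing the cuff, it appears in both languages, and nothing corrects it. A protocol should not depend on its operators ignoring it, and anyone repeating the trial would have to contradict the written procedure. The Chinese text that carries the upper-limb site also ends with the ethics committee's review block, so cuffing the leg would depart from the procedure in that text.

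**Conclusion.** The concern holds, and the text must be corrected. As written, the cuff site contradicts the arm names and the stated mechanism, in both language versions. Confidence in that conflict is high.

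The instruction governs both BFRT arms, 20-30 of 30-45 participants. If it is followed literally, one of the three pairwise contrasts (BFRT alone versus control) loses its intended active difference, and a second (BFRT plus IASTM versus control) loses its BFRT component. If every operator cuffed the exercised leg, no contrast is harmed and the fault is confined to the document. The text alone cannot settle which of these applies.

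**What to change.** 1. The investigator confirms the intended site, and whether one or both legs are cuffed. The second point needs an answer because the Experimental Group exercises include plank and deep squat, which ordinarily load both legs.
2. On confirmation, Research process and methods is changed to place the cuff on the proximal one-third of the exercised lower limb. In 研究过程及方法, 上肢 becomes 下肢 and the exercised side is specified.
3. The ethics committee is notified of the correction.
4. Project Deadline gives trial dates of 20/11/2023 to 30/12/2023, so sessions may already have been delivered. In that case, record the site actually used for each participant in the two BFRT arms, report the counts (including any that cannot be recovered), and describe the intervention accordingly.

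The cost is a one-line correction in each language and an ethics notification. If sessions have been delivered, one further item is recorded for 20-30 participants; this takes more work if it must be reconstructed afterwards, since the plan describes no session log that captures cuff site. Sample size and visits do not change.

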# Research object

Select students majoring in sports dance who have chronic ankle instability and undergo five tests, including balance test, single leg standing, Trendelenburg test, balance test, dynamic balance test, Anterior Drawer test, and Y-Balance test. If two or more tests meet the positive test, it is determined that chronic ankle instability is present, Can be included in the experimental subjects. This experiment has been approved by the Ethics Review Committee of the Medical College of Wuhan Sport University.

**Table 1 Inclusion and Exclusion Criteria** 

Standard	Inclusion Criteria	Exclusion Criteria	
Age	118-35 years old	under 18 years old or above 35 years o	
Course Of	Suffering from chronic ankle instability	Acute ankle injury or no joint injury	
Disease	symptoms that last for at least 3 months		
CAIT score	The CAIT score is 24 points or less.	CAIT score above 24 points	
Functional	Two or more tests tested positive for ankle	Failed ankle function screening	
screening	joint function screening before the		
	experiment		
Structural	No structural joint lesions or congenital	Structural lesions or congenital ankle	
inspection	ankle deformities,	deformities present in the ankle joint	
Medical	Have not undergone ankle surgery or have	Have undergone ankle surgery or have obvious	
History	external injuries	injuries or wounds	
Health	No serious heart, lung, nervous system or	Serious heart, lung, nervous system or other	
Condition	other systemic diseases	systemic diseases	
Agree to	Limited athletic ability, unable to complete	Disagree to participate in the study, or inability	
participate in	research tasks	to understand and comply with the research	
research		protocol	

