Instrument Assisted Soft Tissue Mobilization (IASTM) is a physical therapy technique that utilizes specially designed tools (such as metal or plastic scraping boards) to assist in the treatment of soft tissue problems [24]. Mainly used in rehabilitation medicine, sports medicine, and plastic surgery, it is used to handle tension, adhesion, pain, and motor dysfunction of muscles, fascia, and

tendons [25, 26, 27]. The edge design of IASTM special tools can loosen adhesions in tissues, improving their elasticity and plasticity. Regulating pathological areas through neural pathways, reducing pain and improving neurological function [28]. And different types of treatment tools improve the accuracy of treatment, promote blood circulation, accelerate the rehabilitation process, improve tissue elasticity, expand joint range of motion, and have lower risks and complications compared to invasive surgery [29,30,31]. Studies have shown that IASTM can significantly improve lower limb joint function, reduce pain, and increase range of motion [19, 28].

Therefore, in order to further optimize the rehabilitation process of CAI, this study designed a comprehensive rehabilitation training program that combines blood flow restriction training (BFRT) with ankle balance training, ankle peripheral reinforcement training, and IASTM physical release. BFRT was chosen because it has the adaptability to generate muscle strength at lower loads, providing a relatively low-risk approach for rehabilitation. The combination of ankle balance training and reinforcement training, as well as the physical release of IASTM, is expected to play a synergistic role in promoting the rehabilitation process. Through in-depth research, it is expected to provide more effective and comprehensive rehabilitation plans for sports dance athletes, improve their rehabilitation speed and effectiveness, and better safeguard their health and career.

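### Table 1 does not clearly exclude a past limb clot, or symptomatic or treated limb-vascular disease, although two of three arms train under a blood-flow-restricting cuff

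*Combined protocol and SAP*

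**What the plan says.** Research process and methods randomises 30-45 participants to three arms of 10-15: blood flow restriction training (BFRT) with IASTM, BFRT alone, and traditional strength training. In the two BFRT arms a limb cuff is worn during the ankle exercises, and its stated purpose is "to improve muscle strength and endurance by restricting blood flow". The background under Basic information describes the effect of BFRT in athletes with chronic ankle instability: "Under low load resistance exercise, the oxygen saturation of the calf muscle group is significantly reduced". The same background presents BFRT as "providing a relatively low-risk approach for rehabilitation", and ties that to the lower training load rather than to the cuff.

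Table 1 has one general-health row. Its exclusion cell opens "Serious heart, lung, nervous system or other" and goes on to systemic diseases; the matching inclusion cell carries the same seriousness qualifier and ends "other systemic diseases". The Medical History exclusion begins "Have undergone ankle surgery or have obvious" and continues to injuries or wounds. Screening under Research object is functional: "If two or more tests meet the positive test, it is determined that chronic ankle instability is present". The potential-risks section (潜在风险描述) says that BFRT may cause muscle fatigue and so worsen pain, and that exercise intensity is controllable and can be adjusted to circumstances.

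**The concern.** Restricting circulation in a limb is how the intervention is meant to work. One would therefore expect eligibility to ask about earlier trouble in the limb circulation. Table 1 is specific about the ankle (surgery, wounds, structural lesions, deformity) but handles everything vascular through one catch-all that turns on the word serious. A clot that has resolved is a past event, and an investigator need not class it as a current serious systemic disease. Limb-vascular disease that is symptomatic or treated, yet not judged serious, falls outside the qualifier.

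What is at stake is participant safety. A dancer with such a history could be enrolled in line with Table 1 and, with equal arms, would have a two-in-three chance of cuffed training. No estimate, test or sample-size figure is affected.

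**Working it through.** The plan gives no figure to reproduce on this point. The check is a reading of the eligibility text, then a count of exposure, then a scale calculation on an assumed prevalence.

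**Step 1: what each part of the plan excludes.**

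| Source | Covers | Reaches a resolved limb clot, or symptomatic or treated limb-vascular disease not judged serious? |
|---|---|---|
| Table 1: age, course of disease, CAIT score, functional screening, agreement to participate | Age, ankle symptoms, ability and willingness | No |
| Table 1: structural inspection | Lesions or deformity of the ankle joint | No |
| Table 1: medical history | Ankle surgery, obvious injuries or wounds | No |
| Table 1: health condition | Serious heart, lung, nervous or other systemic disease | Only if the investigator reads it that way |
| Research object and the Chinese recruitment section | Balance and ankle tests | No |
| Pre-intervention evaluation (Research process and methods) | CAIT, FAAM, range of motion | No |
| Potential risks (潜在风险描述) | Fatigue, worse pain, adjustable intensity | No; acts after enrolment |

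Of eight Table 1 rows, none clearly excludes these histories and one might. Neither Research process and methods nor Experimental Group states a cuff pressure, so no visible pressure limit makes up for thin screening.

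**Step 2: exposure to the cuff.**
- Cuffed participants: 2 × 10 = 20 to 2 × 15 = 30, out of 30-45, which is two thirds.
- Sessions each: one weekly for 4-6 weeks gives 4-6. The Process paragraph instead sets six weeks "with a training frequency of 2 sessions per week and each session lasting 20-30 minutes", which gives 2 × 6 = 12.
- Cuffed sessions in total: 20 × 4 = 80 to 30 × 12 = 360. This measures exposure across all cuffed participants, almost none of whom would have a relevant history. It does not measure harm.

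**Step 3: scale under an assumed prevalence p of an uncovered history.** The documents give no value for p; 0.1% to 1% is an assumption. Expected number = n × p. Chance of at least one = 1 − (1 − p)^n.

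| p (assumed) | Expected, n = 20 | Expected, n = 30 | Chance of at least one, n = 20 | Chance of at least one, n = 30 |
|---|---|---|---|---|
| 0.1% | 0.02 | 0.03 | 2.0% | 3.0% |
| 0.5% | 0.10 | 0.15 | 9.5% | 14.0% |
| 1% | 0.20 | 0.30 | 18.2% | 26.0% |

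At the top of the range (n = 30, p = 1%), the chance of none or one is 0.99^30 + 30 × 0.01 × 0.99^29 = 0.740 + 0.224 = 0.964. So even there, zero or one person is the likely result.

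**The case against.** The strongest objection is that the hazard is not in the documents. They report lower calf-muscle oxygen saturation as part of how the training works, and nowhere link it to clotting or to danger after a resolved clot. That stands. The link is clinical reasoning from a cuff that restricts limb blood flow, and the list of histories has to be confirmed by clinicians.

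Second, the catch-all extends to other systemic disease. A known serious clotting disorder could be excluded under it, and some investigators might treat a past thrombosis as evidence of one. That also stands, and it is why the gap is described as not clearly excluded. A reader might infer that Table 1 has no vascular safeguard at all; the wording does not support that.

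Third, there is mitigating text. The risk section says intensity is adjustable, and Quality Assurance says problems will be corrected promptly. Both operate once someone is training; neither decides who is enrolled.

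Fourth, not everything can be seen. The consent pages were removed, and the ethics opinion at the end of the document is not legible. Health questions or safety conditions there could screen such dancers in practice. So a reader should not infer that participants were left uninformed of vascular risk. Table 1 would still lack the criterion.

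Finally, the numbers are small, and the fix does not close the whole gap: disease that is asymptomatic and untreated stays eligible. Both are true. The second is deliberate, so that minor varicose veins do not exclude a dancer.

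**Conclusion.** The concern holds in limited form. With 20-30 of 30-45 participants in a cuff arm, Table 1 does not clearly exclude a resolved limb clot, or symptomatic or treated limb-vascular disease not judged serious, and no other visible text does so.

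A reader might go further and infer that participants were, or would be, harmed. The documents do not support that: they give no event rate, and the 26% upper figure is the chance of enrolling someone with a history, at an assumed prevalence, not the chance of injury. Among 18-35-year-old dance students the number affected is probably zero or one.

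The conclusion rests on two assumptions: that these histories matter for cuff use, and, for scale only, a prevalence of 0.1% to 1%. It is a low-frequency safety precaution, worth taking because it is nearly free. It has no bearing on the analysis.

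**What to change.** Add one exclusion row to Table 1, applied to all three arms before randomisation so that the arms stay comparable:

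- previous or current venous thrombosis of a limb;
- known clotting disorder;
- diagnosed arterial or venous disease of a limb that is symptomatic or under treatment.

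Have the study's clinicians confirm the list. Say limb rather than leg or arm, so that the row holds wherever the cuff is placed. Add the matching risk to the potential-risks section if the removed consent pages do not already state it.

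The cost is three yes/no history questions at the pre-intervention evaluation, one table row and at most one sentence on risk. No test or device is needed. The downside is an occasional dancer not enrolled: under the same assumed prevalence, 30 × 0.001 = 0.03 to 45 × 0.01 = 0.45 expected among all participants. Project Deadline puts the end of recruitment and of the trial in 2023; if enrolment has closed, the row applies to any further enrolment or reuse of this protocol.
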